## PRÉCIS

### Implementation of MIND at Home Program in Primary Care for Patients Living with Dementia: A Pilot Study

#### Objectives

The primary objective of this pilot study is to embed and test the feasibility of a novel best practice-based approach, MIND at Home, within primary care to enhance and elevate the role of existing primary care staff to Memory Care Coordinators (MCCs), increase primary care access to interdisciplinary collaborative care, and systematically combine the benefits of clinic-based services with home- or telephone/video-based enhanced assessment to support family-centered care planning and implementation for people living with dementia (PLWD) and their care partners. Our overarching goal is to test and establish feasibility, acceptability, fidelity, and sample size/referral rate data for MIND at Home in primary care (PC) to prepare for a future multi-site embedded pragmatic trial.

The secondary objective is to test the feasibility of collecting and validating data from large health systems through the extraction of data on 100 additional patients who will not be enrolled in the intervention but will participate in the data validation arm.

#### Design and Outcomes

Using a pragmatic trial design, *this project will embed and test the feasibility of a novel best practice-based approach*, MIND at Home, within PC to enhance and elevate the role of existing PC staff to Memory Care Coordinators (MCCs), increase PC access to interdisciplinary collaborative care, and systematically combines the benefits of clinic-based services with home- or telephone/video-based assessment to support family-centered care planning and implementation for PLWD and their care partners. Weekly virtual collaborative learning sessions that include geriatric psychiatry consultants augment the PC care team's work to support the development and mastery of, and confidence in, dementia assessment and care management skills at the PC sites. Our *overarching goal* is to test and establish feasibility, acceptability, fidelity, and sample size/referral rate data for MIND at Home in PC to prepare for a future multi-site embedded pragmatic trial.

- Aim 1: Evaluate the feasibility and validity of eligible PLWD identification, referral, and enrollment in a best practice-based dementia care coordination program (MIND at Home) at 3 primary care clinics.
- Aim 2: Evaluate the feasibility, acceptability, and fidelity of implementing MIND at Home in 3 primary care clinics in 2 geographically and demographically diverse integrated health systems.
- Aim 3: Evaluate the feasibility of ascertainment of patient-level outcomes over time using electronic health record (EHR) data.

Embedding a collaborative, best-practice based approach such as MIND at Home into PC is a potentially powerful strategy to organize care, improve quality, reduce costs, and maximize population-level benefit for PLWD. This proposal tests the feasibility of implementing MIND at Home into PC in a racially, ethnically, and geographically diverse PLWD population to prepare for a multisite ePCT to evaluate effectiveness, and eventually to support broader dissemination and uptake in PC.

#### Interventions and Duration

This study will test a single intervention. **Maximizing Independence at Home–MIND at Home (MIND)** is a comprehensive care coordination program born from geriatric psychiatry. This model takes an interdisciplinary, collaborative care approach to care by systematically assessing and addressing a wide range of dementia-care related needs of both PLWD and their care partners that place both at increased

risk for poor outcomes.

The five key program components include: (1) identification of dementia-related needs for the PLWD and care partner, using standardized procedures and definitions, including an in-home or telephone/video assessment by the MCC using the Johns Hopkins Dementia Care Needs Assessment (JHDCNA) (13 domains, 61 items; see [Appendix B](#)); (2) family-centered need-based care planning involving the MCC in collaboration with the PC team, following standard protocol, to address unmet needs and match priorities/preferences of the PLWD and family targeting both medical and non-medical determinants of health relevant for all stages of dementia (including social and environmental needs); (3) implementation of care plans linked with proven practice derived care strategies/interventions (e.g., education, coaching, symptom/need assessment, referrals, care coordination/navigation) by the MCC using standardized proven methods and need-based protocols; (4) care monitoring and plan revision, which include regular contact at least every 30 days; and (5) standardized initial program orientation for MCCs and all PC team members and weekly virtual collaborative learning sessions that include a structured case discussion (de-identified) and a short didactic on a specific care topic. Sessions are attended by geriatric psychiatry to support the PC care team's work and advance dementia assessment and care management capacity at PC sites.

PLWD and their care partners will be enrolled for a total of 3 months.

### **Sample Size and Population**

Using a pragmatic trial design, 150 community-residing PC PLWD will be enrolled in the program, each for a 3-month period. Data on an additional 100 PLWD will be pulled for validation purposes.

## 1 STUDY OBJECTIVES

### 1.1 Primary Objective

The primary objective of this pilot study is to embed and test the feasibility of a novel best practice-based approach, MIND at Home, within primary care (PC) to enhance and elevate the role of existing primary care staff to Memory Care Coordinators (MCCs), increase primary care access to interdisciplinary collaborative care, and systematically combine the benefits of clinic-based services with home- or telephone/video-based assessment to support family-centered care planning and implementation for people living with dementia (PLWD) and their care partners. Our overarching goal is to test establish feasibility, acceptability, fidelity, and sample size/referral rate data for MIND at Home in PC to prepare for a future multi-site embedded pragmatic trial.

### 1.2 Secondary Objective

The secondary objective is to test the feasibility of collecting and validating data from large health systems through the extraction of data on 100 additional patients who will not be enrolled in the study but will serve as a data validation arm.

## 2 BACKGROUND AND RATIONALE

### 2.1 Background on Condition, Disease, or Other Primary Study Focus

PLWD represent some of the highest-need and highest-cost individuals living in the community and PC plays a pivotal in the detection, diagnosis, and delivery of services for this vulnerable population. Despite the availability of a range of evidence-based dementia management and symptom approaches, few American PLWD receive adequate care; embedding effective evidence-based interventions and dementia best practices into PC settings is needed, but not yet widely done. PC is the focus of a new CMS-driven alternative payment model (Primary Care First), designed to improve quality, enhance patient experience of care, and reduce expenditures by increasing patient access to advanced primary care services.

### 2.2 Study Rationale

Recent health policy, research, and payment model developments focusing on PC as the nexus of care, coupled with availability of affordable evidence-based care management approaches for dementia, present a profound and timely opportunity to embed effective supports into PC settings to drive value-based care and transform the way care is delivered for PLWD. **Maximizing Independence at Home—MIND at Home (MIND)** is a comprehensive care coordination program born from geriatric psychiatry. This model takes an interdisciplinary, collaborative care approach to care by systematically assessing and addressing a wide range of dementia-care related needs of both PLWD and their care partners that place both at increased risk for poor outcomes. With strong evidence demonstrating its impact on reduction of unmet needs, delay in transition from home to institutionalized settings, improved quality of life, and cost savings through reductions of hospitalization and skilled nursing use, we propose to embed and implement MIND into PC for the first time. Use of MIND in the context of PC is a strong approach that brings a home- or telephone/video-based component to what is often exclusively clinic-based care delivery. It includes a structured assessment to facilitate dementia care planning that holistically addresses patient and caregiver needs and provides valuable initial and ongoing education designed to build PC team dementia management capacity through regular interdisciplinary collaboratives with dementia experts. The MIND model of care directly aligns with stakeholder priorities: PLWDs' wish to remain in their homes as long as possible (evidence suggests PLWD have higher quality of life at home versus in long term care facilities); care partners' desire to avoid burnout while providing the best care possible for their loved ones; primary care providers' incentives to serve their patients by keeping them healthy with the highest quality of life possible; health systems' financial need to avoid unnecessary hospitalizations and ED visits

in an environment of value-based care; payors' motivation to contain costs; and health officials' impetus to improve population health and reduce health care inequities.

The proposed pilot study builds on five prior studies that developed or evaluated the MIND at Home dementia care coordination model in community settings, including two RCTs (MIND-Pilot: n=303; 2007-2012; an NIA RCT (MIND-RCT; n=302; 2014-2020), and a quasi-experimental CMS Health Care Innovation Award Round 2 demonstration project (MIND-HCIA; n=342; 2014-2018). MIND is designed to help PLWD be healthy at home, addressing dementia-related needs to provide better care, better quality, at lower cost. In addition, MIND is currently being implemented in two operational pilots (Superior HealthPlan Medicaid Texas, 2018-2021 and Johns Hopkins (JH) Home Health Care Group private pay in Maryland). Findings to date are:

- ***Unmet care needs are common, both non-medical and medical.*** Studies consistently show that unmet needs are very common for both PLWD and care partners, and most are non-medical. The most recent pooled analysis (n=646) shows common unmet PLWD needs on the JHDCNA are for home and personal safety (98%), medical care (84%), daily activities/meaningful activities (74%), behavioral management (67%), and legal/advance care planning (58%). Common caregiver needs were memory disorder education and care skills (98%), legal issues (74%), mental health (44%), and informal support (43%). More unmet care needs are related to socio-demographics (e.g., Black race, age), lower quality of life, depression, and care partner burden.
- ***Delay in transition from home and nursing home placement.*** MIND-Pilot showed delayed all-cause transition from home (median 288 extra days, or ~9.5 months, over a median follow-up period of 2 years) compared to the augmented usual care group. In an analysis of the pilot RCT data restricted only to PLWD (total n=265; MIND n=99, control n=166) MIND participants delayed time to LTC transition (e.g., nursing home, assisted living) or death (mean 470 days vs. 506 days, mean difference= 36 days) over 18 months. Adjusted hazard of LTC placement decreased by 38% (HR= 0.62, 95%CI 0.39-0.98, p=0.042).
- ***Reductions in use of acute and institutional care and total spending.*** MIND Pilot and MIND-HCIA showed health care utilization patterns and spending redistribution away from acute/institutional care, towards home-, community- and physician-based services. A sub analyses in MIND-HCIA showed a reduction in total Medicaid spending and slower growth in Medicaid inpatient spending and LTC spending compared to propensity matched controls. A pre-post Poisson regression analyses of a pooled sample of MIND intervention recipients (MIND HCIA+MIND RCT; n=442) showed mean number of hospital admissions decreased by 27% (1-0.73) within one year after baseline (95% CI: 6%, 44%, p=0.01). Rates of ≥1 hospitalization declined 36.8% to 32.5%, a crude rate pre/post reduction of 11.6% (unadjusted).
- ***Improvement in care quality, behavior, and high program satisfaction.*** MIND is associated with decreases in unmet care needs on the JHDCNA, improved quality of life, and reduced time spent with the PLWD (objective caregiver burden)(unadjusted) compared to augmented usual care in RCT. In the MIND HCIA, MIND recipients had fewer overall unmet dementia-related needs (PLWD:  $\beta$ =-19.95, SE 0.7, p<0.0001) and in all subdomains (all p<0.0007), fewer behavioral issues (NPI) ( $\beta$  = -5.16, SE 1.4, p=0.0003), reduced caregiver burden (ZBI short) ( $\beta$  = -1.69, SE 0.6, p=0.0054), and reduced caregiver distress (NPI-Distress) ( $\beta$  = -1.63, SE 0.8, p=0.0347) from baseline to 18 months (within subject, pre-post adjusted mixed models). Program satisfaction data (n=390) show that recipients had high service in all domains.
- ***MIND at Home is potentially cost-effective.*** In MIND-HCIA, cost for delivery of MIND were estimated. A difference-in-differences analysis of Medicaid spending estimated return-on-investment (ROI) for a subgroup of participants with claims data (120 dually eligible MIND participants vs. 360 matched controls). The average cost to deliver MIND per enrollee per month was \$110, or \$1,320 per annum. Medicaid expenditures of dual eligibles grew 1.12 percentage points per quarter more slowly than matched controls. Savings came from slower growth in

inpatient and LTC use. The five-year Medicaid savings were estimated at \$7,052 per beneficiary, a 1.12-fold ROI.

### **3 STUDY DESIGN**

#### **3.1 Overview of study design and procedures**

Using a pragmatic trial design, 150 community-residing PC PLWD will be enrolled and receive MIND coordination services for 3 months to test program recruitment and implementation feasibility in PC practice settings. (An additional 100 patients will serve as a data validation arm to demonstrate the feasibility of collecting and validating data from large health systems and will not be enrolled in the intervention.) Enrollees will be recruited through EHR diagnosis and PC referrals. They will undergo a program intake screen (in-clinic or by phone) with a member of the PC team or the memory care coordinator (MCC) to establish program interest and identify the care partner. Interested and eligible enrollees will receive an office- plus home- or telephone/video-based dementia care assessment by the MCC with input from the PC care team. Assessment will be followed by collaborative family-centered care planning, and care plan implementation by an interdisciplinary PC-based team, supported by regular cased-based learning sessions. The primary (hospital transfers, i.e., admissions, ED visits, observation stays) and secondary outcomes (polypharmacy, antipsychotics, acetylcholinesterase, and memantine) will be obtained from regularly collected EHR data.

#### **3.2 Study population and eligibility**

*Community residing* adults,  $\geq 18$  years, living with dementia and who are actively receiving primary care services at one of the three study primary care practices within two participating health care organizations (HCOs) will be targeted. Active patients are defined by the HCO but typically include patients who have received any type of health care service from the HCO in the past three years. PLWD will be defined using algorithms based on CMS' Chronic Care Warehouse definition of Alzheimer's Disease, Related Dementias, Related Disorders, and Senile Dementia. This definition includes those who have an eligible ICD-9/ICD-10, CPT4, or HCPCS code on any eligible claim (i.e., inpatient, outpatient, SNF, or home health visit or stay) in the past three years, a diagnosis on a patient problem list, or a prescription for a dementia-related medication (see Section 4.1 for list). Eligible PLWD must also have a reliable care partner who speaks English (or a language spoken by the MCC) and who is willing to participate in all study home, telephone, or video visits and related activities. PLWD in crises (e.g., show signs of abuse, neglect, extreme risk of danger to self or others), will be referred to receive appropriate services, but will be excluded from the study.

### **4 SELECTION AND ENROLLMENT OF PARTICIPANTS**

PLWD will be identified in the EHR of their respective HCOs and will be approached in two ways. PLWD who present with their care partners for an outpatient office visit will be invited to participate in the program. After establishing eligibility, dyads can choose to enroll by scheduling an initial home visit or phone/video intake with the MCC. Potential participants will be provided a program information sheet, see Appendix C. Enrollment will begin with an initial needs assessment (JHDCNA) during a home or telephone/video visit. Sites will also identify PLWD in the EHR who meet program eligibility criteria but are not scheduled for a visit. PLWD may be identified and referred from other providers to the study primary care clinics. Care partners/PLWD will be contacted by telephone and invited to enroll in the program using a script, based on local context and cultural adaptation of an existing script developed by the JHU team. To ensure equity, racial minorities and other underserved populations will be prioritized and approached using culturally sensitive processes to ensure a representative sample of participants. Recruitment will be supported with existing MIND outreach and engagement resources. MCCs will seek

to enroll a minimum of seven PLWD every other week for a maximum caseload of 42, to accommodate other non-dementia patients who may be part of the MCC total caseload.

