# 6 STUDY PROCEDURES

All outcomes' data will be collected from the participating HCOs' respective EHRs using existing data regularly collected to provide standard patient care and to monitor quality. Participants enrolled in the

intervention will be ‘flagged’ in the EHR as pilot participants and monitored longitudinally.

AMGA regularly collects data from HCOs on a monthly or quarterly basis for all quality improvement, research, and best practices learning collaborative programs, and has a long history of creating detailed data specifications and reporting templates to which member organizations respond and complete. Participating sites have confirmed their ability to do this for this pilot. Monthly data will be submitted to AMGA at the end of study months three, seven, and 10 (see milestones and timeline). Seven total months of EHR data will be collected from each participant: three months prior to enrollment, three months during the intervention, and one month post program discharge.

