## 9.2 Sample Size and Randomization

The pilot study is not powered to detect significant changes in our selected outcome measures. However, we estimated power, nonetheless. Preliminary studies of the MIND at Home program report a reduction from 1 to 0.73 in number of hospital admissions per year, or a 27% decrease. Our primary outcome is hospital transfers (which includes admissions but also ER visits and observation stays without admissions), but we expect that the relative effect size on this outcome will be similar to hospital admissions alone. Because our observation periods are 3 months (as opposed to 1 year), our assumed base rate is 0.50. To make our power estimates slightly conservative, we will assume an effect size of 25%. Given these factors, the estimated power is 37.5% to detect the effect (Z-test with square root adjustment for low base rates). This low power is primarily caused by the short duration of the intervention per patient in the pilot, making outcome observations (transfers) very rare. In the full trial we will use a 12-month intervention period.

For the full trial, sample size estimates will be based on the primary outcome (hospital transfer rate over 12 months). We intend to implement a cluster-controlled cohort design with a baseline period, which requires specialized power calculations (Hemming et al., 2020). Calculations will assume a Poisson distribution of hospitalization rates, equal cluster sizes, and an equal number of clusters in the treatment and control arms. Because validated estimates of correlations are not available, we will use conservative assumptions for intra-cluster correlation (0.05) and individual autocorrelation (0.2). Baseline hospital transfers are estimated to occur at a rate of 1 transfer per year. Assuming this rate, the study will be powered to detect a 0.2 absolute reduction (20% relative reduction) at greater than an 80% power level. This will require at least 11 clusters in each arm of two study arms, with each practice recruiting approximately 50 patients. Analysis of the full study will make use of mixed-model ANCOVA, controlling for both patient level and cluster level confounding variables.

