## 9.5 Data Analyses

A total of 150 PLWD and their care partners receiving care at one of three primary care practices at two health care organizations will be enrolled in the intervention to maximize the likelihood that this pilot study will support the feasibility, generalizability, and scalability to a full-scale ePCT. Data on an additional 100 patients will be extracted for data validation. Data collected during the pilot study will help inform the full ePCT by testing implementation and data collection procedures. Because patients will be enrolled on a rolling basis, we will establish the measurement periods individually for each patient, e.g., for the primary outcome of hospital transfers, we will measure the number of monthly hospitalizations over a 7-month period: three months prior to enrollment, three months during, and one month post discharge from the program. This will allow us to compare the baseline rate (rate of hospitalizations per 1,000 person-days prior to enrollment) with the hospitalization rate in the three months while the patient is enrolled. We will also collect data from the month following program discharge to assess whether hospitalization rates are maintained. We will follow a similar strategy for the secondary outcome of total number of active medications per month. Only exploratory analysis will be performed on the pilot data due to lack of a comparison/control population and low sample size. Descriptive statistics of the study population characteristics and outcomes will be calculated, including stratification at both the cluster and demographic level to identify potential disparities. Outcomes will be compared between the pre- and post-intervention time periods to estimate the effect size of the intervention and will be evaluated using repeated measures ANOVA, though the sample size of the pilot study may not permit definitive results. The R programming language will be used to carry out analysis. Survey results will be reported using descriptive statistics (means and standard deviations for continuous variables and frequency percent for discrete variables) to summarize individual survey items along with histograms for distributions of variables and bar charts/other charts to present the data. To plan for the full trial, we will conduct exploratory analysis to determine measurement reliability and the rate of missingness of patient level (baseline outcome rates, age, sex, race/ethnicity, and comorbidities) and cluster level covariates.

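### The baseline comparison uses three retrospective EHR months from every participant, but nothing requires or records that the patient was under observation in those months

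*Combined protocol and SAP*

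**What the plan says.** Section 6 sets the data window: "Seven total months of EHR data will be collected from each participant: three months prior to enrollment", then three on program and one after discharge. Section 6.2 says the pre-intervention part is gathered retrospectively from site EHRs. Section 9.5 builds the main comparison on it ("This will allow us to compare the baseline rate", per 1,000 person-days, with the on-program rate), applies a similar approach to active medications, and uses the pre/post contrast to estimate an effect size.

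Entry is broader than the window. Section 3.2 leaves the definition of an active patient to the HCO but says that active patients "typically include patients who have received any type of health care service from the HCO in the past three years". Section 4 adds that "PLWD may be identified and referred from other providers to the study primary care clinics" and that sites will also approach patients with no visit scheduled. Section 6.2.1 accepts a diagnosis or prescription from any time in the patient's EHR history. Section 4.1 requires that the patient be actively receiving primary care at a study practice, but sets no minimum period of prior observation.

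Section 11.3.1.1 describes the transferred data as counts per month, without event dates. Section 10.1 (Aim 3) gives the primary outcome as a rate per 1,000 person-days but does not say which days count as observed.

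**The concern.** A before/during comparison from passive records needs both periods to be observed equally well. The entry rules admit two kinds of patient for whom this may fail. One is new to the HCO, having been referred in. The other is on the active list only because of an old service. For either, a low count in months -3 to -1 may mean that nothing happened, or that the HCO was not in a position to know. The extract has no field that separates the two, so the analysts cannot recover the difference later.

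Two things are at stake. One is the effect size that section 9.5 sets out to estimate. The other is Aim 3, which asks whether patient-level outcomes can be ascertained over time from EHR data. A pilot with that aim should be able to tell a zero from an unobserved month.

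The medication outcome is the more exposed of the two. The intake needs assessment in section 5.1 covers medication administration and adherence, so an empty or outdated list may be completed just as the on-program period begins.

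**Working it through.** **Inputs from the documents.** Section 9.5: n = 150 enrolled. Section 9.2: "Because our observation periods are 3 months (as opposed to 1 year), our assumed base rate is 0.50" transfers per patient, a 25% reduction (0.50 to 0.375), and stated power 37.5% from a Z-test with a square-root adjustment. Significance level and sidedness are not stated; I take two-sided 0.05.

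**Reproducing the plan's figure.** On the square-root scale a Poisson count has variance of about 0.25. With the two periods treated as independent:

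power = Φ[(√0.50 − √0.375) / √(0.25 × 2/150) − 1.96] = Φ[0.0947/0.0577 − 1.96] = Φ(−0.319) = 37.5%.

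This matches, so the same formula is used below.

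**Assumed input.** Let f be the share of baseline person-time that is unobserved. The documents give no value, so a range is shown. Assume for now that unobserved time is counted as zero events, that on-program capture is complete, and that affected patients have the same true rate as the rest. Then

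apparent reduction = 1 − 0.75/(1 − f).

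This does not depend on the base rate; only the power does. The third column uses baseline 0.50(1 − f) against 0.375 with n = 150. The last column drops the unobserved patients, n = 150(1 − f), at the true rates, where the expected reduction stays at 25%.

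| f | Apparent reduction | Power, unobserved counted as zero | Power, observed patients only |
|---|---|---|---|
| 0 | 25% | 37.5% | 37.5% |
| 5% | 21.1% | 26.5% | 35.9% |
| 10% | 16.7% | 17.2% | 34.3% (n = 135) |
| 20% | 6.25% | 5.3% | 31.1% (n = 120) |
| 25% | 0% | 2.5% | 29.5% |
| 30% | 7.1% increase | 1.0% | 27.9% (n = 105) |

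**Relaxing complete on-program capture.** If a share g is also missed on program, apparent reduction = 1 − 0.75(1 − g)/(1 − f).

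- f = g = 20%: 25%, no bias.
- f = 20%, g = 10%: 1 − 0.75 × 0.90/0.80 = 15.6%.

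Only the difference in capture between the periods matters.

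**Medications.** If a share f goes from an empty list to one of m drugs with no change in treatment, the mean rises by f × m. With an assumed m = 8, that is 0.4 at f = 5%, 0.8 at 10% and 1.6 at 20%.

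**The case against.** The strongest reply is that this is an omission and not a demonstrated bias. Much of that stands.

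- **Counting unobserved months as zero is not stated anywhere.** A reader might infer it from the silence, but a person-days rate could leave unobserved time out. What remains is that the plan does not say which days count, and the extract gives the analyst nothing to decide with.
- **Every participant must be actively receiving primary care at a study practice (section 4.1), and the referring providers may be inside the HCO.** This narrows the affected group, perhaps to few patients. It does not set a look-back.
- **Capture need not rise at enrollment.** Outcomes are drawn passively (section 8), no office visits are required (section 6.2.3), and nothing says that coordinator contacts feed the transfer counts. A patient who uses the same hospitals before and after is missed equally, and equal loss cancels. This stands for transfers, and is why the medication outcome is the more likely to be affected.
- **Checks are planned.** Section 9.5 examines missingness of baseline outcome rates, section 10.1 adds a test dataset and chart review, and a 100-patient validation arm examines data quality. But an event that never reached the record shows as an ordinary zero count, and reviewing the same record will not find it. The range and validity checks of section 10.3.2 would also pass it.
- **The analysis is exploratory, with no hypothesis (sections 9.1 and 9.5).** This is true, so lost power matters less than a distorted effect estimate.

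**Conclusion.** The gap is real and worth closing, as an inexpensive improvement. The plan compares a retrospective baseline with the on-program months without requiring or recording observation in that baseline, and date-free monthly counts would hide the problem. If capture rises at enrollment, the bias runs toward showing no reduction. At the plan's 25% effect it would take 10% unobserved baseline to shrink the apparent reduction to about 17%, and 25% to remove it, with no capture before, full capture after and unobserved time counted as zero. All three conditions are assumptions, and so is the share.

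Two stronger readings are not supported. One is that the plan does hide a real reduction: neither the zero-counting nor the rise in capture is documented, and equal loss gives no bias. The other is that too low a baseline rate will be carried into the full trial: section 9.2 sets that rate at 1 transfer per year, and no section says the pilot's pre-enrollment rate will replace it.

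**What to change.** 1. Add to the monthly extract a coverage indicator for months -3 to -1, computed by the site. It needs no dates, so it fits section 11.3.1.1.
2. Prespecify the rule behind it, including recency: for example, an HCO encounter before the window opens and within a stated period before it. Asking only for any earlier encounter would pass a patient last seen nearly three years ago. State also how a patient first seen inside the window is handled.
3. In section 9.5, define observed person-days as covered months only, and treat uncovered months as missing, not zero, for transfers and medications alike.
4. Report how many participants and months are affected. Show the baseline rate and the pre/during comparison both for participants with full look-back coverage and for all participants, since those excluded may differ from the rest.
5. Keep every enrollee in the Aim 1 and Aim 2 results.

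The cost is one extra extract field, a few sentences in section 9.5, and a somewhat smaller comparison set: power of about 34% instead of 37.5% if 10% are excluded.
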